5.6.1.8 Post-surgery discharge

POM Clavien-Dindo Classification to be recorded from surgery completion to point of discharge. Fitness for discharge to be assessed by clinical team blinded to treatment intervention.

5.6.1.9 30 day post-surgery visit

30 day post-operative morbidity (Clavien-Dindo Classification) to be recorded from review of patient notes, from the date of discharge to the 30 days post-surgery, SF-36 and EQ-5D-5L questionnaires to be completed and grip strength (measured using a standard digital grip strength dynamometer) recorded. This visit may take within -3 days and +7 days of the schedule.

Post-operative morbidities re-experienced or worsened from the post-surgery inpatient stay should be re-recorded at the 30 day time point. Otherwise the recording of post-operative complications should not be duplicated.

5.6.1.10 6 week post-surgery to 12 month post-randomisation treatment phase

If a patient's return to exercise/usual activities is delayed due to post-operative complications, they may continue in the study and re-commence the exercise intervention once they are able. The protocol treatment interruption should be noted in the eCRF.

Participants randomised to Arm A will receive:

Information on the location of local exercise facilities and physical activity schemes in their local communities. Patients will be encouraged to comply with current physical activity recommendations of completing 150 minutes of moderate intensity aerobic exercise per week (e.g. brisk walking, cycling etc.), measured at 13-15 on the Borg RPE Scale (Borg 1970), and two sessions of resistance exercise per week.

Patients will also be offered supervised "booster" exercise sessions, approximately monthly until 12 months post-randomisation.

Each session will comprise 6 x 5 minute repetitions at 60-80% of heart rate reserve ($^{\circ}$ 60-80% peak VO₂; Borg RPE Scale 13-15 (Borg 1970) with 2.5 minute rest intervals. There will also be 2 home-based resistance exercise sessions per week.

These sessions will be delivered by a member of the Trial Intervention Team who has had trial specific training to deliver these interventions consistently to all Arm A participants.

Adherence to the exercise programme will be recorded in the eCRF from pedometer data, patient participation/attendance and patient completed exercise diaries. All exercise intervention AEs will continue to be recorded.

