5.10.4.7 Safety Analyses

The safety analysis will be based on the pre-defined population (as above). Summary tables will be presented for incidence rates (number of patients with at least one incidence) of adverse events and SAEs coded according to the section 5.11.3.1 of the protocol.

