5.11.3.1 Safety reporting

The principles of ICH GCP require that investigators and sponsors follow specific procedures when notifying and reporting adverse events or adverse reactions in clinical trials. These procedures are described below.

Table 2: Adverse Event Definitions

Adverse Event (AE)	Any untoward medical occurrence in a patient or clinical trial participant and which does not necessarily have a causal relationship with the trial exercise intervention.	
Adverse Reaction (AR)	Any unintended or untoward response to an investigational intervention	
Serious Adverse Event (SAE) or Serious Adverse Reaction (SAR)	 Any AE that at any dose: results in death is life threatening* requires hospitalisation or prolongs existing hospitalisation** results in persistent or significant disability or incapacity is a congenital anomaly or birth defect or is another important medical condition*** 	

^{*} the term life threatening here refers to an event in which the patient is at risk of death at the time of the event; it does not refer to an event that might hypothetically cause death if it was more severe (e.g. a silent myocardial infarction)

^{**} Hospitalisation is defined as an in-patient admission, regardless of length of stay, even if the hospitalisation is a precautionary measure for continued observation. Hospitalisation for pre-

existing conditions (including the planned surgery/elective procedures that have not worsened as a result of exercise) do not constitute an SAE

*** Medical judgement should be exercised in deciding whether an AE is serious in other situations. Important AEs that may not be immediately life threatening or result in death or hospitalisation, but may seriously jeopardise the participant by requiring intervention to prevent one of the other outcomes listed in the table (e.g. a secondary malignancy, an allergic bronchospasm requiring intensive emergency treatment, seizures or blood dyscrasias that do not require hospitalisation, or development of drug dependency).

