5.11.3.2 Clarifications and Exceptions

The intervention under investigation in Prepare ABC is pre- and post-operative exercise. Surgery is conducted in all patients on the trial as part of routine care. All post-operative morbidity up to 30 days post-operation and readmissions up to 90 days are collected as primary and secondary outcome measures in all patients and are not therefore subject to routine safety reporting.

Adverse events include

- An exacerbation of a pre-existing illness
- An increase in frequency or intensity of a pre-existing episodic event or condition
- A condition (regardless of whether PRESENT prior to the start of the trial) that is DETECTED after trial exercise intervention. (This does not include pre-existing conditions recorded as such at baseline as they are not detected after exercise intervention.)
- Continuous persistent disease or a symptom present at baseline that worsens

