5.11.3.6 Investigator responsibilities relating to safety reporting

All AEs and SAEs whether expected or not, should be recorded in the patient's medical notes and reported in the toxicity section of the relevant eCRF.

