5.11.3.6.2 Causality and Expectedness

The investigator must assess the causality of all serious adverse events in relation to the exercise intervention using the definitions in Table 2. There are 5 categories: unrelated, unlikely, possible, probably and definitely related. If the causality assessment is assessed as unrelated or unlikely to be related the event is classified as an SAE. If the causality is assessed as possible, probable or definitely related then the event is classified as an SAR.

Expectedness is assessed by trained NCTU staff against a list of events produced by the co-Cls.

If the event is classified as 'serious' and assessed as being related to the exercise intervention then an SAE form must be completed and NCTU notified within 24 hours. If the event is classified as 'serious' and assessed as **not** being related to the exercise intervention or is thought to be related to a post-operative morbidity (POM) these should still be reported to NCTU via the relevant eCRF forms.

If an SAE is considered to be related to the exercise intervention then continuation of the exercise intervention should be discussed with the Chief Investigator

Table 3: Causality definitions

Relationship	Description	Event type	
Unrelated	There is no evidence of any Unrelated SAE causal relationship		
Unlikely to be related	There is little evidence to suggest that there is a causal relationship (e.g. the event did not occur within a reasonable time after administration of the trial medication). There is another reasonable explanation for the event (e.g. the participant's clinical condition or other concomitant treatment)	Unrelated SAE	
Possibly related	There is some evidence to suggest a causal relationship (e.g. because the event occurs within a reasonable time after administration of the trial medication). However, the influence of other factors may have contributed to the event (e.g. the participant's clinical	SAR	

	condition or other concomitant	
	treatment)	
Probably related	There is evidence to suggest a	SAR
	causal relationship and the	
	influence of other factors is	
	unlikely	
Definitely related	There is clear evidence to	SAR
	suggest a causal relationship	
	and other possible contributing	
	factors can be ruled out	

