5.11.3.7 Notifications

5.11.3.7.1 Notifications by the Investigator to NCTU

NCTU must be notified of all SAEs related to the exercise intervention within 24 hours of the investigator becoming aware of the event.

Investigators should record any SAEs related to the exercise intervention occurring from the time of randomisation until 12 months post-randomisation, when the exercise intervention stops.

The SAE form must be scanned and sent by email to the NCTU SAE reporting email address:

[contact]

The SAE form must be completed by the investigator (the consultant named on the delegation of responsibilities list who is responsible for the participant's care). In the absence of the responsible investigator, the SAE form should be completed and signed by a member of the site trial team and emailed as appropriate within the timeline. The responsible investigator should check the SAE form at the earliest opportunity, make any changes necessary, sign and then email to NCTU. Detailed written reports should be completed as appropriate. Systems will be in place at the site to enable the investigator to check the form for clinical accuracy as soon as possible.

The minimum criteria required for reporting an SAE are the PIN and date of birth, name of reporting investigator and sufficient information on the event to confirm seriousness. Any further information regarding the event that is unavailable at the time of the first report should be sent as soon as it becomes available.

Participants must be followed up until clinical recovery is complete and laboratory results have returned to normal or baseline values, or until the event has stabilised. Follow-up should continue after completion of protocol treatment and/or trial follow-up if necessary. Follow-up SAE forms (clearly marked as follow-up) should be completed and emailed to NCTU as further information becomes available. Additional information and/or copies of test results etc. may be provided separately. The participant must be identified by trial number, date of birth and initials only. The participant's name should not be used on any correspondence and should be blacked out and replaced with trial identifiers on any test results.

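### The rules on which AEs and SAEs to record do not agree, which risks under-recording in Arm C

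*Protocol*

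**What the plan says.** The broad rule is in 5.11.3.6: "All AEs and SAEs whether expected or not, should be recorded in the patient's medical notes", and also in the eCRF. It has no restriction by arm or by cause. The AE definition in 5.11.3.1 agrees with it, since an AE is an occurrence that "does not necessarily have a causal relationship with the trial exercise intervention". Section 5.11.3.6.2 asks for the SAE form within 24 hours when a serious event is judged related to the exercise. For a serious event that is judged unrelated, "or is thought to be related to a post-operative morbidity (POM) these should still be reported to NCTU via the relevant eCRF forms".

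Narrower wording appears in two places. Section 5.11.3.7.1 says: "Investigators should record any SAEs related to the exercise intervention occurring from the time of randomisation until 12 months post-randomisation". Section 5.6.1.10, on the phase from 6 weeks after surgery to 12 months after randomisation, says under Arm A and again under Arm B: "All exercise intervention AEs will continue to be recorded". Its Arm C paragraph has no AE sentence.

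The schedule of assessments (Table 1) has one AE row. It is not split by arm, and it is qualified as applying only where relevant, without saying to whom.

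On analysis, 5.10.4.5 puts every randomised Arm C patient in the safety population, and 5.10.4.7 promises summary tables of "incidence rates (number of patients with at least one incidence) of adverse events and SAEs", not restricted to related events. Section 5.11.3 gives the DMC safety data for each arm.

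**The concern.** The analysis sections assume AE and SAE data collected alike in all three arms. The recording instructions do not secure that. The narrower sentences are tied to the exercise intervention, which Arm C does not receive, so a site that works from them has little or nothing to enter for a control patient. A site that works from 5.11.3.6 enters everything.

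The pooled incidence in each arm would then depend partly on which section each site followed, and the effect would differ by arm. That affects the final safety tables, and also the DMC, which is asked to advise on stopping if there are concerns about harm. Events that were never recorded cannot be restored by a later analysis plan, so the matter belongs in the protocol.

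**Working it through.** The documents give no AE or SAE rates, so there is no figure to reproduce. The check sets the sections side by side.

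| Section | Events covered | Arms | Period stated in words |
|---|---|---|---|
| 5.11.3.6 | All AEs and SAEs | No limit | None |
| 5.11.3.6.2 | Unrelated serious events, via eCRF | No limit | None |
| 5.11.3.7.1 | SAEs related to the exercise | No limit, but tied to the exercise | Randomisation to 12 months |
| 5.6.1.10 | AEs of the exercise intervention | A and B mentioned, C silent | 6 weeks post-surgery to 12 months, by context |
| Table 1 | AEs, with a qualifier | Not split | A span of visits |
| 5.10.4.5 and 5.10.4.7 | All AEs and SAEs tabulated | A, B and all of C | Not stated |

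**Serious events.** 5.11.3.6 and 5.11.3.6.2 together cover related and unrelated SAEs in every arm. What is missing is a stated period for the unrelated ones, because the only stated period is attached to related SAEs.

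**Non-serious events.** 5.11.3.6.2 does not help here, since it deals only with serious events. In Arm C these events rest on 5.11.3.6 and the qualified schedule row. In Arms A and B there is also the reminder in 5.6.1.10. This is the weaker part of the protocol.

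**A lesser point.** One of four listed AE types in 5.11.3.2 is a condition "that is DETECTED after trial exercise intervention". Arm C has no such anchor. The other three types apply to Arm C without difficulty, so this adds little.

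**What mixed practice would do.** Let p_X be the true proportion of Arm X with at least one non-exempt AE, and let s be the share of patients at sites using the narrower wording (taken as equal across arms, since randomisation is stratified by centre). Let r be the share of exercise-arm patients with an event who have at least one judged related. Assume that no Arm C event is judged related, because causality is assessed against the exercise intervention.

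- Recorded in Arm A: p_A × [(1 − s) + s × r]
- Recorded in Arm C: p_C × (1 − s)
- Recorded difference: (1 − s) × (p_A − p_C) + s × r × p_A

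A true difference is shrunk by the factor (1 − s), and an artefact of s × r × p_A is added. If all sites follow 5.11.3.6, then s = 0 and both effects vanish. The protocol gives none of p, s or r, so no value can be put on the result.

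**The case against.** The strongest reply is that the sections can all be obeyed together. 5.11.3.7.1 is headed as notification to NCTU, and the sentence at issue lies between the 24-hour rule and the instructions for emailing the SAE form. It can be read as setting the scope and period of the expedited route, with unrelated SAEs going through the eCRF under 5.11.3.6.2. The Arm A and Arm B paragraphs of 5.6.1.10 describe what those arms receive, and silence under Arm C does not exempt it from 5.11.3.6. Serious outcomes are also collected in all arms by other routes: 30-day morbidity, 90-day readmission and mortality, and secondary care use over 12 months (5.10.5).

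Much of this stands. A reader might infer that sites are told to record exercise-related events alone, in Arms A and B alone, so that Arm C must score zero. The protocol does not support that. No section contains such a restriction, 5.11.3.6.2 keeps unrelated serious events reportable, 5.10.4.5 includes all of Arm C, and 5.11.3 does not confine the DMC data to exercise-related AEs.

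The reply leaves three gaps. 5.11.3.7.1 speaks of recording, in a sentence separate from the notification rule. It is the only text that states a period; the schedule row spans visits but does not settle which events or which arms. And neither 5.11.3.6.2 nor the outcome data supply non-serious AEs in Arm C, in particular before surgery and during the later exercise phase.

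**Conclusion.** The point holds as an inconsistency in recording scope, with a risk of under-recording in Arm C. It is clearest for non-serious Arm C events and for the recording period of unrelated events in any arm. For SAEs the risk is smaller, because an explicit all-cause route exists.

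Whether the tables in 5.10.4.7 would be distorted depends on how many sites follow the narrower wording. If none do, there is no distortion. If some do, the arms are not comparable. The documents do not allow the extent to be estimated, and neither a spurious excess in the exercise arms nor a missed true excess can be quantified from them. The passages should be reconciled, but the inconsistency does not undermine the trial's design.

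**What to change.** In 5.11.3.7.1, state that all AEs and SAEs not exempted by the protocol are recorded in the eCRF, on the same terms in all three arms, from randomisation to 12 months post-randomisation. Limit the related-only wording there to the SAE form and the 24-hour notification. In 5.6.1.10, use one AE sentence for Arms A, B and C in place of the present wording under A and B. Leave the exemptions and the 24-hour rule as they are, and label the safety tables to match the recording rule.

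The cost is wording in two sections and slightly more data entry for Arm C. The eCRF route is already required by 5.11.3.6 and 5.11.3.6.2.

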5.11.3.7.2 NCTU responsibilities

Medically qualified staff at NCTU and/or the medical Chief Investigator (CI or a medically qualified delegate) will review all SAE reports received.

NCTU is undertaking the duties of trial sponsor and is responsible for the reporting of intervention related SAEs to the REC as appropriate.

NCTU will keep investigators informed of any safety issues that arise during the course of the trial.

5.11.4 Quality Assurance and Control

5.11.4.1 Risk Assessment

The Quality Assurance (QA) and Quality Control (QC) considerations for the PREPARE-ABC trial are based on the standard NCTU Quality Management Policy that includes a formal Risk Assessment, and that acknowledges the risks associated with the conduct of the trial and proposals of how to mitigate them through appropriate QA and QC processes. Risks are defined in terms of their impact on: the rights and safety of participants; project concept including trial design, reliability of results and institutional risk; project management; and other considerations.

QA is defined as all the planned and systematic actions established to ensure the trial is performed and data generated, documented and/or recorded and reported in compliance with the principles of GCP. QC is defined as the operational techniques and activities performed within the QA system to verify that the requirements for quality of the trial related activities are fulfilled.

5.11.4.2 Central Monitoring at NCTU

NCTU staff will review electronic Case Report Form (CRF) data for errors and missing key data points. The trial database will also be programmed to generate reports on errors and error rates. Essential trial issues, events and outputs, including defined key data points, will be detailed in the PREPARE-ABC Data Management Plan.

5.11.4.3 On-site Monitoring

The frequency, type and intensity of routine and triggered on-site monitoring will be detailed in the PREPARE-ABC Quality Management and Monitoring Plan (QMMP). The QMMP will also detail the procedures for review and sign-off of monitoring reports.

5.11.4.3.1 Direct access to participant records

Participating investigators must agree to allow trial related monitoring, including audits and REC review by providing access to source data and other trial related documentation as required. Participant consent for this must be obtained as part of the informed consent process for the trial.

5.11.4.4 Trial Oversight

Trial oversight is intended to preserve the integrity of the trial by independently verifying a variety of processes and prompting corrective action where necessary. The processes reviewed relate to participant enrolment, consent, eligibility, and allocation to trial groups; adherence to trial interventions and policies to protect participants, including reporting of harms; completeness, accuracy and timeliness of data collection; and will verify adherence to applicable policies detailed in the Compliance section of the protocol. Independent trial oversight complies with the NCTU trial oversight policy.

In multi-centre trials this oversight is considered and described both overall and for each recruiting centre by exploring the trial dataset or performing site visits as described in the PREPARE-ABC Quality Management and Monitoring Plan.

5.11.4.4.1 Trial Management Team

The Trial Management Team (TMT) will be set up to assist with developing the design, co-ordination and day to day operational issues in the management of the trial, including budget management.

5.11.4.4.2 Trial Management Group

A Trial Management Group (TMG) will be set up to assist with developing the design, co-ordination and strategic management of the trial. The membership, frequency of meetings, activity (including trial conduct and data review) and authority will be covered in the TMG terms of reference.

5.11.4.4.3 Independent Trial Steering Committee

The Independent Trial Steering Committee (TSC) is the independent group responsible for oversight of the trial in order to safeguard the interests of trial participants. The TSC provides advice to the CI, NCTU, the funder and sponsor on all aspects of the trial through its independent Chair. The membership, frequency of meetings, activity (including trial conduct and data review) and authority will be covered in the TSC terms of reference.

5.11.4.4.4 Independent Data Monitoring Committee

The Independent Data Monitoring Committee (IDMC) has access to accumulating comparative data between each arm of the study. The IDMC is responsible for safeguarding the interests of trial participants, monitoring the accumulating data and making recommendations to the TSC on whether the trial should continue as planned. The membership, frequency of meetings, activity (including review of trial conduct and data) and authority will be covered in the IDMC terms of reference. The IDMC will consider data in accordance with the statistical analysis plan and will advise the TSC through its Chair.

5.11.4.4.5 Trial Sponsor

The role of the sponsor is to take on responsibility for securing the arrangements to initiate, manage and finance the trial. When an institution is the trial sponsor and has delegated the duties as sponsor to NCTU, the delegation will be confirmed via a signed letter of delegation.

5.12 COVID-19 Impact and Adaptation

The emergence of the COVID-19 pandemic caused disruption to recruitment and greatly impacted the way in which cancer patients interact with the NHS along their care pathway. Recruitment was suspended at all sites by 23 March, 2020. In order to minimise face-to-face contact upon re-opening recruitment, Arm A (hospital supervised exercise) will be suspended until sites are able to offer this intervention.

During the suspension period, patients will be recruited into a 2-arm randomised control trial consisting of Arm B (home based intervention) and Arm C (treatment as usual) to 90% power with the two primary outcomes as originally planned: change in quality of life at 12 months and post-operative morbidities at 30 days.

6 Ethics and Dissemination

